2.3 Limitations and Assumptions

This is a pilot study and thus generalizability to the broader population of patients who have ATTR-CA and are on stabilizer and/or silencer treatment, is unknown. Further, the patients were already on stabilizer and/or silencer therapy at the time of PET/CT scan, for varying duration.

3. PATIENT NUMBERING

Each patient will be uniquely identified in the study by a combination of the site number and screening number. The site number will be assigned by the coordinating site. The screening number will be assigned sequentially.

4. ADVERSE AND SERIOUS ADVERSE EVENTS

4.1 Adverse Events Definition

An AE is any untoward medical occurrence in a human subject, including any abnormal sign (for example, abnormal physical exam or laboratory finding), symptom, or disease temporally associated with the subject's participation in the research.

4.2 Serious Adverse Event (SAE) Definition

An SAE is any untoward medical occurrence related to study participation that:

1. Results in death.
2. Is life-threatening (an event which places the patient at immediate risk of death from the event as it occurred. It does not include an event that had it occurred in a more severe form might have caused death).
3. Requires in-patient hospitalization or prolongation of existing hospitalization.
4. Results in persistent or significant disability or incapacity.
5. Is a congenital abnormality or birth defect.
6. An important medical event that may not be immediately life-threatening or result in death or hospitalization but may jeopardize the patient and may require intervention to prevent one of the other outcomes listed in the definition above (e.g. events include allergic bronchospasm requiring intensive treatment in an emergency room or at home, blood dyscrasias, convulsions, or the development of drug dependency or abuse).

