4.3 Collecting and Reviewing Adverse Event and Outcome Information

During 7 day and 28 day follow-up visits, whether in person or via telephone, the subjects will be asked about medically relevant changes in their health since the previous visit including hospitalization, and whether those hospitalizations were related to cardiovascular health.

The study team will record AE information for start dates/times occurring any time after informed consent is obtained until 28 days after the time of imaging agent infusion.

To assess relationship of an event to study procedure, the following guidelines are used:

- Unrelated
- Unlikely to be related
- Possibly related
- Probably related
- Definitely related

All adverse events must have their relationship to study participation, expectedness and severity of the event assessed by a qualified investigator, upon reporting of the event. These determinations will be made according to the professional opinion of the investigator using the package insert of

the imaging agent and the investigators assessment will be entered into the Redcap data collection software by research staff. All AEs will be followed by the investigator until the events are resolved, the subject is lost to follow-up, the condition is stabilized, or the AEs are otherwise explained.

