5. ADVERSE EVENT REPORTING

5.1 Reporting to the Sponsor

The principal and participating investigator will report every serious adverse event (SAE) to the study sponsor, Attralus, as soon as possible, but no later than 48 hours after becoming aware of the event via phone, email or facsimile, and will complete the new SAE field on the Redcap database as soon as possible but no later than 48 hours after becoming aware of the event. The principal investigator will document the time of their awareness of the SAE in the study subject's binder.

A participating investigator will also provide follow-up information on the SAE once new or updated information is available. The follow-up information will be added to the Redcap SAE field, as a follow-up to the initial entry.

Non-serious adverse events will be recorded on the Adverse Event Form. All non-serious entries related to study drug must be completed by the participating investigator within 5 business days.

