5.2 Reporting to the IRB

Unanticipated Problem (UP):

An unanticipated problem is any incident, experience or outcome involving risks to subjects or others in any human subjects' research that meets all of the following criteria:

- Unexpected (in terms of nature, severity or frequency) given (a) the research procedures that are described in the IRB-approval protocol and informed consent document, and (b) the characteristics of the subject population being studied;
- Related or possibly related to participation in such research (e.g., there is a reasonable possibility that the incident, experience or outcome may have been caused by the procedures involved in such research); and
- Suggests that the research places subjects or others at a greater risk of harm (including physical, psychological, economic or social harm) than was previously known or recognized.

Reports of all events (including follow-up information) that meet the definition of an unanticipated problem posing risk to subjects or others must be submitted to the IRB within one week (5 business days) following the occurrence of the unanticipated problem or the investigator's acquiring knowledge of the unanticipated problem in accordance with IRB policy. Additionally, the investigator will submit a summary of all unanticipated problems that occurred since the beginning of the study at the time of continuing review.

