5.3 Reporting to the FDA

Suspected Adverse Reaction:

In accordance with 21 CFR 312.32(a), a suspected adverse reaction (SAR) means any adverse event for which there is a reasonable possibility that the drug caused the adverse event.

The IND Sponsor will be responsible for all communication with the FDA and will report to the FDA, any adverse event that is serious, unexpected and for which there is reasonable possibility that the drug caused the adverse event. These must be reported to the FDA as soon as possible, but no later than 15 calendar days after the Sponsor determines that the information qualifies for reporting. Any fatal or life-threatening SARs will be reported to the FDA as soon as possible, but no later than 7 calendar days after the Sponsor determines that the information qualifies for such reporting.

All other serious adverse events will be included in the IND annual reports that are to be submitted to the FDA within 60 days of the anniversary date of the IND each year.

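### Section 4.2 builds relatedness into the SAE definition, so a death or hospitalisation judged unrelated falls outside the 48-hour reporting in 5.1

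*Combined protocol and SAP*

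**What the plan says.** Section 4.1 defines an adverse event by timing: an abnormal sign, "symptom, or disease temporally associated with the subject's participation in the research".

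Section 4.2 does not carry that over. Its stem reads "An SAE is any untoward medical occurrence related to study participation that", followed by six criteria that include death and in-patient hospitalisation. The condition stands in the stem, so it governs all six.

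Section 4.3 treats causality as a separate judgement on every event: "All adverse events must have their relationship to study participation, expectedness and severity of the event assessed by a qualified investigator". It provides five grades, from unrelated to definitely related, and a collection window from consent to 28 days after infusion. At the day 7 and day 28 contacts, patients are asked about changes in health "including hospitalization, and whether those hospitalizations were related to cardiovascular health".

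Section 5.1 requires every SAE to be reported to the company named there as study sponsor "no later than 48 hours after becoming aware of the event via phone, email or facsimile", and the REDCap SAE field to be completed in the same time. For other events it says "All non-serious entries related to study drug must be completed by the participating investigator within 5 business days".

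Section 5.2 sends an event to the IRB only if, among other conditions, it is "Related or possibly related to participation in such research". Section 5.3 sends to the FDA "any adverse event that is serious, unexpected and for which there is reasonable possibility that the drug caused the adverse event", with limits of 15 and 7 calendar days. The remaining serious adverse events go into the IND annual report.

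**The concern.** Whether an event is serious is a matter of outcome. Whether it was caused by the study is a matter of opinion. Under 4.2 the second decides whether the first is recognised. If the investigator judges a death unrelated, the event is not an SAE by this definition, and the 48-hour rule, which is written for SAEs, has nothing to act on. The investigator's own causality opinion therefore decides whether the company receives prompt notice, with no stated opportunity for it to look at that opinion in time.

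Such events are foreseeable. The patients have cardiac amyloidosis, and 4.3 asks specifically about hospitalisations and whether they were cardiovascular. An admission for the underlying heart disease could readily be judged unrelated to a single tracer dose.

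There is also a tension over sequence. Section 4.3 has relatedness assessed when the event is reported, while 4.2 makes relatedness a precondition for reporting it as an SAE. Section 4.2 does not say which of the five grades satisfy that precondition, so two investigators could handle an event graded unlikely to be related differently and both comply.

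**Working it through.** No arithmetic beyond a count applies. The check follows one event, a death or hospitalisation graded unrelated, through each reporting rule, under the current wording and again with the relatedness condition removed from 4.2.

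| Rule | Condition in the rule itself | Current wording | Condition removed from 4.2 |
|---|---|---|---|
| 5.1, 48-hour report to the company | Event is an SAE | Does not apply | Applies |
| 5.1, 48-hour REDCap SAE field | Event is an SAE | Does not apply | Applies |
| 5.1, 5 business days | Non-serious and related to study drug | Does not apply (not related) | Does not apply (serious, and not related) |
| 5.2, IRB, 5 business days | Includes at least possible relation to participation | Does not apply | Does not apply |
| 5.3, FDA, 15 days | Includes reasonable possibility of drug causation | Does not apply | Does not apply |
| 5.3, FDA, 7 days | Suspected adverse reaction, fatal or life-threatening | Does not apply | Does not apply |
| 5.3, IND annual report | Remaining SAEs | Unclear | Applies |

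Reading the table:

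1. Only the two 48-hour actions depend on 4.2 alone. For this event they go from 0 of 2 applying to 2 of 2.
2. The other four short-deadline rules give the same answer in both columns. They exclude the event by their own terms, so 4.2 is not the reason.
3. The annual report is unclear for a specific reason. Its line uses the SAE term that 4.2 restricts. It also covers what is left after events with a reasonable possibility of drug causation are taken out, so it contemplates SAEs not caused by the drug. Those could still be events related to participation in some other way, so the line does not settle the case of an event unrelated to participation altogether.
4. No other section restores the 48-hour report. Section 5.4 covers serious and unexpected events associated with the drug. Section 6.2 mentions SAE reports but adds no definition. Section 6.5 sets general database entry within five days of a visit, which is not a safety notice, and it does not say who shares the database.
5. The Data Analysis Plan (2.2.9) describes no safety analysis, so no planned analysis changes.

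**The case against.** The first defence is that the stem of 4.2 is loose wording for an event during participation. The neighbouring sections weigh against this: 4.1 says temporal association where it means timing, and 4.3 speaks of relationship to participation where it means causality.

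The second is that the event is not lost. This stands. All AEs from consent to 28 days after infusion are recorded, graded, entered in REDCap and followed, and a research worker who does not perform the procedures reviews the study data. That limits the consequence, but none of it is prompt notice to the company named in 5.1.

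The third concerns scope. A reader might infer that 4.2 takes such an event out of every expedited route. The documents do not support this. Sections 5.2 and 5.3 filter on causality in their own right, and the expedited FDA text speaks of an adverse event that is serious rather than using the SAE term that 4.2 restricts. Counting every deadline in 5.1 to 5.3 against 4.2 would overstate its effect.

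The fourth concerns who is left uninformed. A reader might infer that the site's opinion keeps the party that starts the FDA clocks from hearing of the event. That is conditional. The front page names the institution as sponsor and lists a Sponsor-Investigator, 5.1 names a company, and the documents do not say who holds the IND. If the Sponsor-Investigator holds it, that party may already know of the event.

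**Conclusion.** The point holds in limited form. Section 4.2 merges seriousness with causality, against the structure of 4.1, 4.3 and 5.3. The effect is that a serious event judged unrelated escapes both 48-hour actions in 5.1, and its place in the IND annual report is uncertain. The IRB and expedited FDA rules are not affected, the event is still collected and followed, and no analysis changes.

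This rests on a literal reading of the stem of 4.2 and on the absence of any passage that restores reporting; both were checked against the text. The number of affected events is unknown, because the documents give no background rate of death or hospitalisation for these 10 patients. The change should be made because it closes a gap in safety reporting at almost no cost, although the study's results do not depend on it.

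**What to change.** In 4.2, delete the four-word relatedness condition from the stem, so that an SAE is any AE as defined in 4.1 that meets one of the six criteria within the existing collection window. In the 48-hour rule of 5.1, add *regardless of causality*.

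Keep relatedness as the separate 4.3 assessment, and leave the causality conditions in 5.1 (non-serious events), 5.2 and 5.3 as they are. It may be tempting to add a sentence to 4.3 saying which grades count as related for all of these rules. That should not be done. The rules refer to different things (study drug in 5.1, participation in 5.2, the drug in 5.3), and 5.3 leaves the determination to the Sponsor, so one common cut-off would not fit them. Once the condition leaves 4.2, the 48-hour rule needs no cut-off.

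The cost is two short wording changes and possibly a few more 48-hour reports in a 10-patient study.

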4.3 Collecting and Reviewing Adverse Event and Outcome Information

During 7 day and 28 day follow-up visits, whether in person or via telephone, the subjects will be asked about medically relevant changes in their health since the previous visit including hospitalization, and whether those hospitalizations were related to cardiovascular health.

The study team will record AE information for start dates/times occurring any time after informed consent is obtained until 28 days after the time of imaging agent infusion.

To assess relationship of an event to study procedure, the following guidelines are used:

- Unrelated
- Unlikely to be related
- Possibly related
- Probably related
- Definitely related

All adverse events must have their relationship to study participation, expectedness and severity of the event assessed by a qualified investigator, upon reporting of the event. These determinations will be made according to the professional opinion of the investigator using the package insert of

the imaging agent and the investigators assessment will be entered into the Redcap data collection software by research staff. All AEs will be followed by the investigator until the events are resolved, the subject is lost to follow-up, the condition is stabilized, or the AEs are otherwise explained.

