CLINICAL STUDY PROTOCOL

Title: A Follow-Up Study to Monitor Therapeutic Response in Transthyretin Cardiac Amyloidosis Using Amyloid Reactive Peptide ¹²⁴I-evuzamitide (AT01) PET/CT

Protocol Version: 2.0

Protocol Date: October 26, 2023

ClinicalTrials.gov: NCT05635045

Sponsor: Columbia University Irving Medical Center
Clinical Cardiovascular Research Laboratory for the
Elderly (CCRLE)
[name]
[name]

Sponsor-Investigator: [name]
[contact]

Collaborating Investigators: [name], PhD
Columbia University Irving Medical Center

[name], DO
Columbia University Irving Medical Center

STUDY SYNOPSIS

Protocol Title	Title: A Follow-Up Study to Monitor Therapeutic Response in Transthyretin Cardiac Amyloidosis Using Amyloid Reactive Peptide ¹²⁴ I-evuzamitide (AT01) PET/CT
Protocol Number	1.0
Design	
This is a single center, prospective cohort study that is evaluating the ability of ¹²⁴I-evuzamitide PET scanning to serially assess and quantify TTR stabilizer and TTR silencer response in the heart in ATTR-CA. 10 subjects will be recruited from our pilot study that have a baseline ¹²⁴I-evuzamitide PET/CT showing cardiac uptake, who are on TTR stabilizer and/or silencer therapy. Data generated from this study will provide amongst the first evidence of changes in myocardial amyloid load on PET/CT imaging with disease modifying therapy and provide preliminary data to support larger investigations in this arena.
 
Consented eligible patients will undergo a single ¹²⁴I-evuzamitide PET scan. Clinically available demographic, clinical and phenotypic data that is collected as part of routine clinical care will be used to characterize the type, severity, and stage of ATTR-CM. Bloodwork, electrocardiograms, and echocardiograms will be performed at the time of the scan.

Study Sites	This study is to be conducted at Columbia University Irving Medical Center.
Time on Study	The duration of patient participation in this study is 31 days.
Primary Objective	To assess and quantify TTR stabilizer and TTR silencer response in the heart in ATTR-CA.
Sample Size	10 patients will be included in this study.

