Inclusion and Exclusion Criteria	
10 Participants from the current study on ATTR treatment will be recruited to one cohort.
 
Overall Inclusion Criteria:
 
 1. Must have given written informed consent (signed and dated) and any authorizations required by local law and be able to comply with all study requirements. 2. Were enrolled in the initial pilot using ¹²⁴I-Evuzamitide, on ATTR stabilizer and/or silencer therapy. Able to understand and sign the informed consent document after the nature of the study has been fully explained. 3. TTR genotype shown to be either Val122Ile or wild type. 
The presence of any of the following excludes eligibility for enrollment in this study:

	
 1. Primary amyloidosis (AL) or secondary amyloidosis (AA). 2. Active malignancy or non-amyloid disease with expected survival of less than 1 year. 3. Heart failure, in the opinion of the investigator, primarily caused by something other than amyloidosis. 4. Ventricular assist device. 5. Impairment from stroke, injury or other medical disorder that precludes participation in the study. 6. Disabling dementia or other mental or behavioral disease. 7. Enrollment in a clinical trial not approved for co-enrollment. 8. Continuous intravenous inotropic therapy. 9. Inability or unwillingness to comply with the study requirements. 10. Chronic kidney disease requiring hemodialysis or peritoneal dialysis. 11. Patients taking heparin, or heparin derivatives (e.g. low molecular weight heparins) for anticoagulation. 12. Other reason that would make the subject inappropriate for entry into this study.
Aims	
The specific aim is to determine if ¹²⁴I-evuzamitide PET/CT scanning can:
 
(1) Serially quantify TTR cardiac amyloid load as measured after 1 year of TTR stabilizer and/or silencer treatment.

Safety Assessments	
The safety of study participants will be evaluated by:
 
 1. Assessment of adverse events (AEs), including serious adverse events (SAEs). 2. Vital sign measurements (blood pressure, pulse rate, and respiratory rate). 3. Physical examinations

SCHEDULE OF ACTIVITIES

The following table summarizes the activities to be performed at each of the designated study visits. Details of the different procedures can be found in subsequent sections of this manual.

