2.2.3 Time on Study

The duration of patient participation in this study is 31 days (for one month follow-up to assess for safety and 3 days of potassium iodide administration prior to PET scanning).

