2.2.5 Patient Recruitment

The subjects have been selected from among subjects who underwent 124I-evuzamitide PET/CT scanning previously. All necessary follow-up care or communication of adverse events or incidental findings will either take place as part of the clinical care of the enrolled subjects or be communicated in writing and via telephone with the physician.

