2.2.9 Data Analysis Plan

Descriptive statistics will be used to summarize subjects' demographics and clinical features. The subjects will be re-randomized for the readers and for quantification. The quantification will be performed using PMOD, and 3 different physicians will be performing quantification individually to verify reproducibility. PET scans will be interpreted by two readers blinded to the clinical information. The organ-specific radioactivity data will be expressed as the mean and standard deviation (SD) of three independent ROIs. The coefficient of variation (COV) will be expressed as (SD/mean)*100.

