4.4 Stopping Study Procedure Due to Adverse Event

In the use of this procedure there have been no reports of serious adverse reactions. Nevertheless, the injection and scan procedure will be stopped, and the results will be marked as incomplete if there are any adverse reactions during its administration as part of this study. The adverse reactions that will lead the investigators to stop the ^{124}I -evuzamitide PET scan include but are not limited to the following events: hypotension, fever, chills, nausea, vomiting and dizziness, as well as hypersensitivity reactions such as itching and various skin rashes.

The scan will also be stopped in cases of severe cardiac symptomology such as: chest pain, shortness of breath, palpitations, tachycardia. In such cases, other study procedures may be continued.

In addition to the planned 7 day and 28 day follow-up phone visits, subjects will be asked to contact the investigators if any additional adverse or allergic reactions are noted within the first 24 hours following the injection. If any such events are reported, the principal investigator will determine if they are potentially related to the administration of the imaging agent. Appropriate clinical care will be advised for any events determined by the investigator to be related to the scanning injection, and information about the reactions will be reported as described below.

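### The last safety call may be made up to four days before the adverse-event recording period ends, with no planned contact afterwards

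*Combined protocol and SAP*

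**What the plan says.** Section 4.3 sets the recording period by onset date: from informed consent "until 28 days after the time of imaging agent infusion". For the follow-up contacts, the same section says that "the subjects will be asked about medically relevant changes in their health since the previous visit", so each contact looks backwards only.

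The Schedule of Activities has two follow-up safety calls after the scan visit, at Day 7 (2 days either side) and Day 28 (4 days either side). Nothing is scheduled after the second call. The protocol does not say whether the infusion day is Day 0 or Day 1.

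Three other statements bear on how a late event could reach the study team:

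- Section 4.4 asks patients to contact the investigators themselves about reactions that "are noted within the first 24 hours following the injection".
- Section 2.2.5 says that communication of adverse events will "take place as part of the clinical care of the enrolled subjects or be communicated in writing and via telephone with the physician".
- Section 4.3 has known adverse events followed until they resolve or stabilise.

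The synopsis lists adverse-event assessment first among three safety evaluations. Both the synopsis and Section 2.2.3 state that "The duration of patient participation in this study is 31 days".

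**The concern.** The recording period and the call window end on different days. A call in the early half of the window follows the schedule, yet it takes place before the recording period closes and cannot ask about what has not yet happened. An event that starts between such a call and the end of the period belongs on the adverse-event list, but the protocol plans no contact that would find it. It would become known only if the patient or a treating physician raised it.

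The two texts do not contradict each other, since an event that reaches the team after an early call can still be recorded. What the protocol lacks is a planned way to learn of it. At stake is the completeness of the adverse-event list over the period that the protocol itself chose.

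**Working it through.** **Inputs**

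- End of recording: 28 days after infusion (Section 4.3).
- Last call: Day 28, 4 days either side (Schedule of Activities), so 28 − 4 = Day 24 to 28 + 4 = Day 32, which is 32 − 24 + 1 = 9 permitted days.
- Potassium iodide: 3 days before the scan (Sections 2.2.3 and 2.2.7).
- Patients: 10 (Section 2.2.4).
- Half-life: 96 hours (Section 2.2.7).

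**The plan's own figure.** 3 days of potassium iodide + 28 days of follow-up = 31 days, which reproduces the stated duration. This fits the infusion day as Day 0, so that convention is used below and Day 1 is shown as the alternative.

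**Days without planned contact.** With Day 0, gap = max(0, 28 − call day). With Day 1, the period ends on Day 29, so gap = max(0, 29 − call day).

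| Call on | Gap, infusion = Day 0 | Gap, infusion = Day 1 |
|---|---|---|
| Day 24 | 4 | 5 |
| Day 25 | 3 | 4 |
| Day 26 | 2 | 3 |
| Day 27 | 1 | 2 |
| Day 28 | 0 | 1 |
| Days 29–32 | 0 | 0 |

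With Day 0, a Day 28 call made earlier in the day than the infusion is still short by some hours.

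**Across the ten patients.** Post-infusion patient-days: 10 × 28 = 280.

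- Worst case, all calls on Day 24: 10 × 4 = 40; 40/280 = 14.3%.
- Worst case against the full recording period: this starts at consent and includes at least the 3 potassium iodide days, so it is at least 3 + 28 = 31 days per patient, or 310 in total. The share is at most 40/310 = 12.9%.
- Calls spread evenly over the 9 permitted days (assumption): (4 + 3 + 2 + 1)/9 = 1.11 days per patient; × 10 = 11.1; 11.1/280 = 4.0%.
- Best case, all calls on Day 28 or later: 0.
- Worst case with infusion as Day 1: 10 × 5 = 50; 50/280 = 17.9%.

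The documents do not give actual call dates.

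**Plausibility of late tracer effects.** By Day 24, 24 × 24 h / 96 h = 6 half-lives have passed. On physical decay alone, 2⁻⁶ = 1.6% of the activity remains.

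**The case against.** The strongest reply is that this has almost no consequence. The recording rule decides which onsets count, while the window is a tolerance around a nominal Day 28 call, and nothing requires the two to end together. Late tracer effects are unlikely, the PET objective does not depend on adverse events, and the Data Analysis Plan (2.2.9) contains no adverse-event analysis. All of that stands and limits the weight of the point. Even so, Section 4.1 counts any untoward occurrence linked in time to participation, whether or not the tracer caused it, and the calls ask specifically about hospitalisation and whether it was cardiovascular. In patients with cardiac amyloidosis such events can start on any day.

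A second reply is that other routes exist. The clinical-care and physician routes in Section 2.2.5 are real, and the 24-hour request in Section 4.4 does not forbid later reports. The consent pages were not available for review, so further instructions to patients cannot be ruled out. This stands too, but none of these is a scheduled contact, and following a known event to resolution does not detect a new one.

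A third reply is that the percentages describe scenarios. That is fair: 14.3% requires every call on the earliest permitted day, 4.0% rests on an assumed spread, and calls made on target give zero under Day 0. They should be read as a range and not as an expected loss.

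**Conclusion.** The concern holds, as a minor design point and not an error. With the infusion day as Day 0, a compliant call on Days 24 to 27 leaves 4 to 1 days of the protocol's own recording period without planned contact. Over ten patients this ranges from 0 to 40 of 280 post-infusion patient-days, depending on when the calls are made. The conclusion does not depend on the day convention: counting the infusion as Day 1 widens the gap, and even an on-target Day 28 call then falls a day short. No planned estimate changes. It is worth considering because the repair is cheap.

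**What to change.** In the Schedule of Activities, change the last call to **Day 28 (+4 days)** and add a footnote: **Day 0 = day of imaging agent infusion**. Optionally, add that a Day 28 call is made no earlier than the clock time of the infusion, which closes the remaining hours. The stated 31 days can stay as a nominal figure, or the synopsis and Section 2.2.3 can say up to 35 days including potassium iodide, which the current window already permits (3 + 32 = 35).

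The cost is one table entry and one footnote, plus optional wording in two places, with the IRB approval that Section 6.3 requires for an amendment. No visit or procedure is added. Scheduling becomes less flexible: 32 − 28 + 1 = 5 permitted days instead of 9. Participation would run from 3 + 28 = 31 to 35 days, instead of from 3 + 24 = 27 to 35. The maximum does not move, but all the flexibility would then lie at or beyond the stated 31 days.

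A lighter alternative keeps the present window and asks patients, at an early call, to report anything new up to Day 28. That helps, but it still relies on the patient and is not a planned contact.
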